6.4 Randomisation criteria

To be randomised, all randomisation criteria must be answered "yes".

1. BMI corresponding to ≥ 30 kg/m² for adults by international cut-off points and \geq the 95th percentile for age and sex (for diagnosis of obesity).
2. Compliance with run-in procedures and visit schedule as judged by the investigator.
3. PHQ-9 score < 15 at randomisation
4. No suicidal ideation of type 4 or 5 since last visit based on the C-SSRS questionnaire at randomisation

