6.3 Exclusion criteria

For an eligible subject, all exclusion criteria must be answered "no".

1. Pre-pubertal subjects (Tanner stage 1) at screening V2
2. Body weight \leq 60 kg
3. Type 1 diabetes mellitus
4. Calcitonin ≥ 50 ng/L
5. Family or personal history of multiple endocrine neoplasia type 2 (MEN2)
6. Medullary thyroid carcinoma (MTC)
7. History of pancreatitis (acute or chronic)
8. Subjects with secondary causes of obesity (i.e., hypothalamic, genetic or endocrine causes)
9. Treatment with medications within 90 days before screening V2 that, based on the investigator’s judgement, may cause significant weight change. This should also include treatment with any of

the following medications: pramlintide, orlistat, zonisamide, topiramate, lorcaserin, phentermine, bupropion, naltrexone, GLP-1 receptor agonists, or metformin (used as treatment for obesity)

10. Anti-diabetic treatment other than metformin
11. Diet attempts using herbal supplements or over-the-counter medications within 90 days before screening V2
12. Participation in an organised weight reduction program (e.g., Weight Watchers[®]) within 90 days before screening V2
13. Previous surgical treatment for obesity (excluding liposuction if performed >1 year before screening V2)
14. History of major depressive disorder within 2 years before screening V2
15. Any lifetime history of other severe psychiatric disorder (e.g., schizophrenia, bipolar disorder)
16. PHQ-9 score of ≥ 15 at screening V2
17. Any suicidal ideation of type 4 or 5 based on the baseline C-SSRS questionnaire at screening V2
18. Any suicidal behaviour within 30 days before screening V2
19. Any lifetime history of suicidal attempt
20. Uncontrolled treated or untreated hypertension >99th percentile for age and gender in children. If white-coat hypertension is suspected at screening V2, a repeated measurement at V3 prior to other trial-related activities is allowed (last measurement being conclusive)
21. Surgery scheduled for the trial duration period, except for minor surgical procedures, at the discretion of the investigator
22. Subjects with confirmed bulimia nervosa disorder
23. Diagnosis of malignant neoplasms within the last 5 years prior to screening V2 (except basal and squamous cell skin cancer)
24. Known or suspected abuse of alcohol or narcotics
25. Language barrier, mental incapacity, unwillingness or inability to adequately understand or comply with study procedures

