26. Known or suspected hypersensitivity to trial product or related products
27. Previous participation in this trial. Participation is defined as signed informed consent.
28. Subjects from the same household participating in the trial
29. Participation in any clinical trial of an approved or non-approved investigational medicinal product within 30 days before screening V2
30. Female who is pregnant, breast-feeding or intends to become pregnant or is of child-bearing potential and not using an adequate contraceptive method (adequate contraceptive measure as required by local regulation or practice)

For Sweden only: Oral (except low-dose gestagen [lynestrenol and norethisteron]), injectable, or implanted hormonal contraceptives, intrauterine device, intrauterine system (for example, progestin-releasing coil), vasectomized male (with appropriate postvasectomy documentation of the absence of sperm in the ejaculate). Use of contraception is not required for female subjects who have not yet made their sexual debut and/or are not sexually active.

For Belgium only: Highly effective methods of birth control are defined as those, alone or in combination, that result in a low failure rate (i.e., less than 1% per year) when used consistently and correctly; such as implants, injectables, combined oral contraceptives, some intrauterine devices, true sexual abstinence (i.e., refraining from heterosexual intercourse during the entire period of risk associated with the study treatments) or vasectomised partner.

31. Any condition which, in the opinion of the investigator, might jeopardise subject's safety or compliance with the protocol

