8.1.5 Screening failures

A screening failure is a subject who does not fulfil one or more of the inclusion and/or exclusion and/or randomisation criteria. For screening failures the screening failure form in the electronic case report form (eCRF) must be completed with the reason for not continuing in the trial. Serious adverse events (SAE) from screening failures must be transcribed by the investigator into the eCRF. Follow-up on SAEs must be carried out according to Section [12](#). A screening failure session must be made in the IWRS. The case book must be signed.

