8.1.6 Re-screening

Re-screening is NOT allowed if the subject has failed one of the inclusion, exclusion criteria or randomisation criteria, this includes re-sampling if the subject has failed one of the exclusion criteria related to laboratory parameters.

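### Protocol 6.4 repeats the V2 screens for PHQ-9 and suicidal ideation at randomisation but not the screen for suicidal behaviour, so some non-attempt behaviour between V2 and V9 is not barred by name

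*Protocol*

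**What the plan says.** Protocol 6.3 has four numbered exclusions on acute mental-health risk. Number 16 is a PHQ-9 score of 15 or more at V2. Number 17 is "Any suicidal ideation of type 4 or 5 based on the baseline C-SSRS questionnaire at screening V2". Number 18 is "Any suicidal behaviour within 30 days before screening V2". Number 19 is "Any lifetime history of suicidal attempt" and names no visit. Number 31 is a general clause, also without a visit: "Any condition which, in the opinion of the investigator, might jeopardise" the subject's safety or compliance.

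Protocol 6.4 then requires, as criterion 3, "PHQ-9 score < 15 at randomisation" and, as criterion 4, "No suicidal ideation of type 4 or 5 since last visit based on the C-SSRS questionnaire at randomisation". It has no criterion on suicidal behaviour. Protocol 8.4.9.1 agrees with 6.4: the C-SSRS at screening and at randomisation excludes on ideation of type 4 or 5 only.

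SAP 2.5.3 says something different. It describes the C-SSRS at screening/randomisation as part of the exclusion criteria and names suicidal behaviour and previous attempts. It also assigns the baseline version of the form to screening/randomisation and the since-last-visit version to all other visits.

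Under Protocol 8.4.9.3, any suicidal behaviour requires referral to a mental health professional (MHP). Where a psychiatric disorder can be adequately treated, continuing is at the investigator's discretion with the MHP's agreement.

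**The concern.** Section 8.4.9.3 puts a PHQ-9 score of 15 or more, suicidal behaviour and type 4/5 ideation in one list of triggers for mandatory referral. Section 8.4.9 says that both ideation and behaviour must be watched for with weight-loss drugs. Yet at randomisation two of these three signals bar entry by name and the third does not, and the protocol gives no reason.

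The result is an odd ordering in time. Non-attempt behaviour shortly before V2, more than three months before first dose, excludes the subject by name. The same behaviour in the week before first dose does not, unless it comes with something else that does. The subjects are minors, and sites could decide differently on the same event. What is at stake is subject safety and consistent eligibility; the primary analysis, power and type I error are not involved.

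**Working it through.** The plan gives no figure to reproduce. The check compares the criteria side by side and then counts days on the visit schedule.

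**1. Which V2 screens return at V9**

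| Signal | At V2 (6.3) | At V9 (6.4) |
|---|---|---|
| PHQ-9 of 15 or more | No. 16 | Criterion 3 |
| C-SSRS ideation type 4/5 | No. 17 | Criterion 4 |
| Suicidal behaviour, 30 days | No. 18 | None |
| Lifetime attempt | No. 19, no visit named | None |

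Of the three screens tied to V2, two are repeated. The look-back of no. 18 ends at V2, so it covers none of the time from V2 to V9.

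**2. Whether nos. 19 and 31 still apply after V2**

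- Section 8.1.4 has the inclusion and exclusion criteria evaluated before run-in starts.
- Section 8.1.7 names only the randomisation criteria for the check at V9.
- Section 8.1.5, however, says: "A screening failure is a subject who does not fulfil one or more of the inclusion and/or exclusion and/or randomisation criteria".

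The first two suggest that the exclusion criteria are settled before run-in. The third suggests that a failure that arises later still counts. The text does not decide between them.

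**3. What remains without a named bar**

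Start from any suicidal behaviour between V2 and V9 and remove what is already caught:

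- attempts, if no. 19 is read as still applying;
- behaviour with type 4/5 ideation inside the V9 look-back (criterion 4);
- behaviour in a subject whose PHQ-9 score at V9 is 15 or more (criterion 3).

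What is left is non-attempt behaviour without type 4/5 ideation in the look-back and with a PHQ-9 score below 15. For this group the plan provides mandatory referral, MHP agreement where there is a psychiatric disorder, and no. 31 at the investigator's discretion. After randomisation, no discontinuation criterion in 6.5 names suicidal behaviour.

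**4. The days involved**

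Inputs: V2 at week -14, V8 at week -2 and V9 at week 0 (flowchart in Protocol section 2; SAP Table 3-1). The first dose is given at V9 (8.1.7).

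- V2 to V9: 14 × 7 = 98 days.
- Window of no. 18, counted back from V9: 98 to 98 + 30 = 128 days.

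Coverage of the 98 days by a behaviour criterion at V9:

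| Look-back from V9 | Days covered | Share | Days left |
|---|---|---|---|
| Since the preceding visit (V8) | 14 | 14/98 = 14% | 84 |
| 30 days, as in no. 18 | 30 | 30/98 = 31% | 68 |
| Since V2 | 98 | 98/98 = 100% | 0 |

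These are shares of time, not of events or subjects. The documents give no event rate.

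**5. The look-back at V9**

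Criterion 4 in 6.4 asks about the time since the last visit. SAP 2.5.3 assigns the baseline version to randomisation and reserves the since-last-visit version for other visits. The two do not match, so the period that even the existing ideation criterion covers at V9 is uncertain.

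**The case against.** The strongest reply is that this is a deliberate and consistent design. Sections 6.4, 8.4.9.1 and 8.4.9.2 all agree on what is re-checked at randomisation. Several other exclusions tied to V2 are not repeated either (nos. 9, 11, 12, 14 and 29). Behaviour after V2 goes to referral and clinical judgement, as it also does after randomisation, where it does not by itself stop trial product. An investigator who is worried can use no. 31, if it is read as still open, and no. 15 excludes a severe psychiatric disorder without naming a visit.

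Much of this stands. There is a real safety net, and preferring judgement to a hard bar is defensible. It does not explain why behaviour is treated differently from the two signals listed beside it in 8.4.9.3, or why SAP 2.5.3 describes behaviour as exclusion content at randomisation.

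Two stronger readings are tempting and not supported. One is that all suicidal behaviour goes unscreened for 98 days. Criteria 3 and 4 bar part of it, referral is mandatory, and the 98 days measure the interval, not the size of the uncovered group. The other is that the SAP sentence closes the gap. A SAP does not set eligibility, and 6.4 has no such criterion, so the sentence shows only that the documents disagree.

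**Conclusion.** The point holds in a narrow form. Non-attempt suicidal behaviour in the nominal 98 days from V2 to V9, without type 4/5 ideation in the V9 look-back and with a PHQ-9 score below 15, is not barred by name. It is handled by mandatory referral and otherwise by judgement. The same behaviour 98 to 128 days before first dose is barred.

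A reader might infer that new attempts are also left open. The documents do not establish this: the lifetime wording of no. 19 together with 8.1.5 points to coverage, 8.1.4 and 8.1.7 point the other way, and the matter is one of reading.

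The conclusion rests on nominal visit timing and on a distinction between behaviour and attempt that the documents do not define. If behaviour is largely read as attempt, the uncovered group shrinks. The number of subjects affected is unknown and probably small. No analysis is affected. This is a minor safety point and a cheap improvement.

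**What to change.** Add a fifth criterion to Protocol 6.4: *No suicidal behaviour or suicide attempt within 30 days before randomisation, based on the C-SSRS at randomisation.* This mirrors no. 18. Naming attempts also settles, for those 30 days, whether no. 19 still applies. A stricter option is *since screening V2*, which covers all 98 days and joins the window of no. 18, giving 30 + 98 = 128 days barred by name. That is longer than the protocol's own 30-day standard, so the choice is the sponsor's.

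Add behaviour to 8.4.9.1. State in 6.4 and SAP 2.5.3 which C-SSRS version and look-back apply at V9.

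The cost is one line and matching wording. The C-SSRS is already completed at randomisation, so no visit or questionnaire is added, provided that the version used at V9 records behaviour over the chosen look-back; the form itself is not in the documents. There may be a few more screening failures, and these are final: "Re-screening is NOT allowed if the subject has failed one of the inclusion, exclusion criteria or randomisation criteria".

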6.5 Criteria for premature discontinuation of trial product

Efforts must be made so that subjects attend and complete all scheduled visit procedures. Randomised subjects should stay in the trial irrespective of lack of adherence to randomised treatment, lack of adherence to visit schedule or missing assessments. Only in case a subject or subject's LAR decline any further contact with the site in relation to the trial this will be considered as withdrawn from the trial.

The subject may be prematurely discontinued from trial product, at the discretion of the investigator, due to a safety concern. The subject must be prematurely discontinued from trial product if the following applies:

1. Safety concern (not covered by any of below criteria) or unacceptable intolerability to trial product, as judge by the investigator.
2. Included in the trial in violation of the inclusion and/or exclusion criteria and/or randomisation criteria
3. Pregnancy
4. Intention of becoming pregnant
5. In case of code break (see Section [11.1](#))
6. Suspicion of pancreatitis (see Sections [8.4.10.5](#) and [8.4.11](#)). Subjects may restart on trial product should the suspicion not be confirmed.
7. Diagnosis of medullary thyroid carcinoma
8. Weight loss attempts other than what is agreed with the dietitian as part of the trial intervention
9. If diabetes treatment other than healthy nutrition, physical activity and metformin addition is initiated.

10. Initiation of treatment with medications that, based on the investigator's judgement, may cause significant weight change. This should also include treatment with any of the following medications: pramlintide, orlistat, zonisamide, topiramate, lorcaserin, phentermine, bupropion, naltrexone, GLP-1 receptor agonists, or metformin (used as treatment for obesity)
11. Anti-diabetic treatment other than metformin
12. Initiation of diet attempts using herbal supplements or over-the-counter medications
13. Inadequate psycho- and/or pharmaco therapeutic treatment of a subject's psychiatric disorder (see Section [8.4.9.3](#))
14. The subject and/or the subject's LAR refusal of referral to a mental health professional (MHP) and it, in investigator's opinion, is unsafe for the subject to continue in the trial (see Section [8.4.9.3](#))
15. Simultaneous participation in another clinical trial of an approved or non-approved investigational medicinal product
16. The subject treated with 0.6 mg trial product experiences persistent intolerance as judged by the investigator

See Section [8.1.10](#) for procedures to be performed for subjects discontinuing trial product prematurely.

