8.1.10 Premature discontinuation of trial product

If a subject prematurely discontinues trial product, the investigator must aim to undertake procedures similar to those for the end of treatment (V25) as soon as possible, and a follow-up visit (V26) two weeks later.

The subjects must be asked to attend additional visits depending on when the trial product discontinuation takes place during the trial:

- If the trial product is discontinued before V19 subjects must be asked to attend three additional visits (V19x, V25x and V30x) taking place weeks 30, 56 and 82 after randomisation, respectively.
- If the trial product is discontinued after V19 and before V25 subjects must be asked to attend two additional visits (V25x and V30x) taking place weeks 56 and 82 after randomisation, respectively.

The primary reason for premature discontinuation of trial product must be specified on the end of trial form in the eCRF, and final drug accountability must be performed. A treatment discontinuation session must be made in the IWRS.

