8.4.11 Suspicion of acute pancreatitis

In case of acute, severe persistent abdominal pain leading to a suspicion of acute pancreatitis, the trial product should promptly be interrupted until the presences of pancreatitis can be excluded. See Section [6.5](#). Appropriate additional examinations must be performed. Measurement of amylase and lipase must be done locally. If acute pancreatitis is ruled out, subject should resume dosing at the discretion and direction of the investigator. Trial product dose changes must be recorded in the eCRF.

Pancreatitis is confirmed if as a minimum 2 of 3 criteria are met:

- Severe acute abdominal pain
- Blood amylase and/or lipase >3x upper limit of normal (ULN)
- Characteristic findings on relevant imaging (e.g., computerised axial tomography/magnetic resonance imaging/ultrasound)

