17.4.1.2 Safety endpoints

Adverse events

AEs will be summarised for the safety analysis set separately for three periods:

- Run-in period: defined as events with onset date between V2 (included) and the first day of trial product administration (not included).
- In-trial period: defined as events with onset date between the first day of trial product administration and the last study visit.
- On-treatment period: defined as events with onset date between the first day of trial product administration and whatever comes first: a) 14 days after the last day on trial product , b) follow-up visit (V26 for subjects with trial product discontinued), or c) last study visit (subjects withdrawn without follow-up visit).

A treatment-emergent adverse event (TEAE) is defined as an event that occurs in the “on-treatment” period.

The AEs will be coded using the most recent version of the Medical Dictionary for Regulatory Activities (MedDRA). They will be presented in terms of the number and percentage of subjects with at least one event, the number of events and the event rate per 1000 years. AEs in the screening period (prior to randomisation) will be presented in listings.

Hypoglycaemic episodes

Hypoglycaemic episodes will be summarised descriptively by severity and treatment in terms of the number and percentage of subjects with at least one episode and the total number of episodes. Separate summaries will be made by severity (the ISPAD criterion for severe hypoglycaemia⁴⁹). In

the same way as for AEs, there will be separate summaries for the “in-trial” and “on-treatment” periods. Hypoglycaemic episodes in the screening period will be presented in listings.

Classification of Hypoglycaemia

Treatment emergent: hypoglycaemic episodes will be defined as treatment emergent if the onset of the episode occurs on or after the first day of trial product administration, and no later than 14 days after the last day on trial product.

Nocturnal hypoglycaemic episodes: are episodes occurring between 23:00 and 07:00 both inclusive.

[figure not shown]
Hypoglycaemic episodes are classified according to ISPAD’s definition of severe hypoglycaemia⁴⁹ as well as the Novo Nordisk classification of hypoglycaemia; see [Figure 17–1](#) and the ADA classification of hypoglycaemia; see [Figure 17–2](#)).

Novo Nordisk classification of hypoglycaemia in paediatrics

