In order to improve gastrointestinal tolerability of liraglutide, a weekly dose-escalation scheme will be used during the initial 4-8 weeks. In contrast to the scheme used for adult subjects, for adolescent subjects, the trial product dose will be escalated only if the previous dose is tolerated (as judged by the investigator). Furthermore, to resolve tolerability issues, the investigator is allowed to lower to the previously given dose or to prolong a dose step for one additional week (see Section [8.1.8.1](#)). Subjects treated with trial product should be advised of the potential risk of dehydration, renal impairment and acute renal failure, in relation to gastrointestinal AEs and take precautions to avoid fluid depletion.

Hypoglycaemic episodes will be assessed in this trial as part of routine safety monitoring. If a subject develops T2DM during the trial, he/she will be allowed to remain in the trial if glycaemic control can be achieved with healthy nutrition, physical activity and metformin.

Subjects with a history of acute or chronic pancreatitis will be excluded from trial participation. Trial participants will be informed of the characteristic symptoms of acute pancreatitis. Furthermore, serum lipase and amylase activity levels will be monitored on a regular basis during the course of the trial. If pancreatitis is suspected, the trial product should promptly be interrupted until the presences of pancreatitis can be excluded (see Section [8.4.11](#)) and appropriate treatment should be initiated. Subjects that are diagnosed with acute pancreatitis must have their trial product discontinued. Subjects with a personal or family history of MTC and subjects with MEN2 are excluded from this trial. In addition, subjects with a screening calcitonin (a specific biomarker for C-cell activation) level ≥ 50 ng/L will be excluded from the trial as hormone concentrations above this threshold are indicative of C-cell neoplasia. During the trial, calcitonin levels will be measured at pre-specified trial visits and levels above ULN will be flagged by the laboratory, and reported to the investigator and Novo Nordisk.

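### Suspected pancreatitis is both a mandatory discontinuation and an interruption in the protocol; on the discontinuation route, the on-treatment rule can leave adverse events after a restart out of the TEAE count

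*Protocol*

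**What the plan says.** **Clinical handling (protocol).**

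- Section 6.5 introduces its list with "The subject must be prematurely discontinued from trial product if the following applies". Item 6 is suspicion of pancreatitis, with the added sentence "Subjects may restart on trial product should the suspicion not be confirmed". The section closes by referring discontinued subjects to 8.1.10 and makes no exception for item 6.
- Section 8.1.10 asks for V25-type procedures as soon as possible, V26 two weeks later, the extra visits V19x, V25x and V30x as applicable, and final drug accountability. It also states: "A treatment discontinuation session must be made in the IWRS".
- Section 8.4.11 says of the same event that "the trial product should promptly be interrupted until the presences of pancreatitis can be excluded", and then: "If acute pancreatitis is ruled out, subject should resume dosing at the discretion and direction of the investigator".
- Section 18.1 also describes interruption on suspicion and ties discontinuation to diagnosis: "Subjects that are diagnosed with acute pancreatitis must have their trial product discontinued".

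**Analysis definitions (protocol 17.4.1.2).** The on-treatment period for adverse events runs from first dose to the earliest of three dates: (a) 14 days after the last day on product, "b) follow-up visit (V26 for subjects with trial product discontinued"), or (c) the last study visit for subjects withdrawn without follow-up. A TEAE is an event in that period. Treatment-emergent hypoglycaemia has a different end: "no later than 14 days after the last day on trial product", with no V26 limb. The in-trial period runs from first dose to the last study visit.

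The SAP (2.4.1.2 and 3.3) does not redefine the on-treatment period. The TEAE count is one of the endpoints marked for public disclosure in protocol 4.2.2.2.

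**The concern.** Item 6 itself allows restart, so the conflict is not between restarting and not restarting. It is between a full close-out of treatment and a temporary stop. A site that reads 6.5 with 8.1.10 closes treatment in IWRS and holds V26. A site that reads 8.4.11 or 18.1 does neither.

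The statistical consequence comes from limb (b). It assumes that once product has been discontinued and V26 held, exposure is over. A subject who restarts breaks that assumption. Nothing in either document says that the on-treatment period reopens at restart, or which V26 counts if there are two. Two sites handling the same event differently would therefore give different TEAE periods for the same exposure. The subjects affected are those re-exposed after a pancreatitis suspicion, where a later event on drug is of particular safety interest.

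**Working it through.** The plan states no figure on this point, so there is nothing to reproduce. The check applies the 17.4.1.2 rule literally to a subject who restarts.

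**Inputs from the documents**

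- Day 1 is randomisation, V25 is Day 393 and V26 is Day 407 (SAP Table 3-1). 407 − 393 = 14 days.
- V26 is held two weeks after the V25-type visit (protocol 8.1.10).
- The on-treatment period ends at the earliest of limbs (a), (b) and (c) (protocol 17.4.1.2).

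**Assumptions, not in the documents**

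- The suspicion arises at week 4, 12, 30 or 51, and the V25-type visit takes place on the day of stopping.
- Restart follows 3, 7, 21 or 28 days after stopping.
- The subject then doses through Day 393.

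**Formulas**, for suspicion at week w and restart r days after stopping:

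- stop day = 1 + 7w; early V26 = stop day + 14; restart day = stop day + r
- limb (a) = 393 + 14 = Day 407
- period end = min(407, early V26)
- post-restart on-drug days = 393 − restart day + 1
- days inside the period = max(0, period end − restart day + 1); days outside = the remainder

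**Worked case, w = 12, r = 3.** Stop on Day 85, early V26 on Day 99, restart on Day 88. On-drug days after restart: 393 − 88 + 1 = 306. Inside: 99 − 88 + 1 = 12. Outside: 306 − 12 = 294.

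**Same case with r = 28.** Restart on Day 113, after V26. On-drug days: 393 − 113 + 1 = 281. Inside: 0. Outside: 281.

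| Suspicion at week | Stop day | Period closes under limb (b) | Closes under limb (a) | Post-restart on-drug days outside (r = 28 to r = 3) |
|---|---|---|---|---|
| 4 | 29 | Day 43 | Day 407 | 337–350 |
| 12 | 85 | Day 99 | Day 407 | 281–294 |
| 30 | 211 | Day 225 | Day 407 | 155–168 |
| 51 | 358 | Day 372 | Day 407 | 8–21 |

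If restart comes before V26, only the days up to V26 stay inside: 12 for r = 3 and 8 for r = 7. If restart comes after V26, none do.

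**Interruption route.** Under 8.4.11 with no V26 at the interruption, limb (a) governs, the period ends at Day 407 and no on-drug days are lost.

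**Hypoglycaemia.** The definition has only the limb (a) type of cut-off, so it runs to Day 407 in every row. On the 8.1.10 route, the same subject is on treatment for hypoglycaemia and off treatment for all other adverse events.

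**After the fix.** If limb (b) is the V26 following the final dose, it cannot fall before Day 393. Post-restart on-drug days outside the period are then 0 in every row.

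**The case against.** Sections 6.5 no. 6, 8.4.11 and 18.1 can be read as one sequence under two labels: stop, investigate, resume if pancreatitis is ruled out. Limb (b) is confined to subjects with product discontinued, and a subject who has resumed can reasonably be read as outside it, so that limb (a) governs and nothing is lost. This stands to the extent that the loss is conditional. It requires that the site follows 8.1.10, that the early V26 is held, and that the analyst applies limb (b) to it. It does not remove the ambiguity: 6.5 gives item 6 no exemption from 8.1.10, and 17.4.1.2 does not say that discontinued means permanently discontinued.

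Three stronger readings are tempting, and the documents do not support them.

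- *That the events, including a later true pancreatitis, disappear.* Adverse events are collected to week 82 (protocol 12.2), pancreatitis has its own event form (8.4.10.5), and the in-trial summaries have no V26 cut-off. The event leaves the on-treatment summaries only.
- *That SAP Table 2-2 has no place for a restarted subject.* Its classifying column is whether the subject is on randomised treatment at the landmark visit, which already settles the class; only the type descriptions are loosely worded. The primary imputation in SAP 2.3.2 also pools the two available types as source and the two missing types as targets, so the class would not change the result.
- *That a restarted subject cannot be supplied with drug.* Protocol section 10 lists no restart session in IWRS, but it does list data change and refers to separate user manuals. Silence in the protocol does not show that restart is impossible.

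**Conclusion.** The inconsistency is real. Section 6.5 no. 6 with 8.1.10 requires a premature discontinuation and its procedures on suspicion alone, while 8.4.11 and 18.1 describe an interruption. Followed as written on the 8.1.10 route, limb (b) gives a wrong TEAE period for a subject who restarts, and a period that disagrees with the one for hypoglycaemia.

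The size per subject depends on timing: from 8–21 on-drug days for a suspicion at week 51 to 337–350 for one at week 4, and none on the interruption route. These figures rest on the assumed timelines above. The documents do not give the number of subjects with a suspicion who restart. It is probably small, since 18.1 reports few pancreatitis events in the weight-management trials, although suspicions may outnumber confirmed events. No trial-level effect on the TEAE count can therefore be computed.

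The primary efficacy analysis is done on the in-trial period (SAP 3.1) and is not touched by this rule. The point is worth correcting because it concerns a disclosed safety endpoint in subjects re-exposed after a safety signal.

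**What to change.** 1. Reconcile protocol 6.5 no. 6, 8.1.10, 8.4.11 and 18.1. State whether a suspicion counts as an interruption or a premature discontinuation, and whether it triggers the 8.1.10 visits and the IWRS discontinuation session. Which clinical rule applies is for the sponsor to decide; this point takes no view on it.
2. In protocol 17.4.1.2, define limb (b) as the V26 that follows the subject's final dose of trial product, so that a V26 held before or during a restarted course does not end the on-treatment period. This works whichever clinical handling is chosen in step 1. If the protocol is no longer open to amendment, the same clause can go in SAP 3.3.

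SAP Table 2-2 needs no change for this purpose.

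The cost is a short clarification in the clinical sections and one clause in the analysis definition. No new visits or data are needed: dose levels, dates of change and reasons are already recorded in the eCRF (protocol 8.1.8.3), and 8.4.11 requires dose changes around a suspicion to be recorded there too.
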